4.0 Study Endpoints

4.1 The primary endpoints are interest in contraception and contraception initiation. Secondary endpoints are location of contraception counseling and initiation, and contraceptive method choice.

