12.0 Local Number of Subjects

- 12.1* It is expected that 450 participants will be recruited for the study.
- 12.2* It is expected that 1,000 adolescents will be eligible for the study from 2021-2023. We estimate that 45% will agree to participate.

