17.0 Data Management* and Confidentiality

17.1 *Describe the data analysis plan, including any statistical procedures or power analysis.*

For our first objective, the dependent variables are interest in receiving contraception counseling during a hospital stay and interest in starting a contraceptive during a hospital stay.

- We will examine interest in receiving contraception counseling during hospitalization among female adolescents hospitalized with mental health disorders by assessing the proportion of participants who answer yes to the following survey question “Interest in learning more about contraception during your hospital stay”.
- We will examine interest in initiating contraception during hospitalization among female adolescents hospitalized with mental disorders by assessing the proportion of participants who answer yes to the following question “Interest in starting a contraceptive during your hospital stay”.
- We will perform univariate descriptive analyses on all variables.
- We will perform bivariate analysis to explore the relationship between variables “Interest in learning more about contraception during your hospital stay” and “Interest in starting a contraceptive during your hospital stay” using 2 X 2 contingency tables.

PROTOCOL TITLE: Evaluation of Contraception Care @ Behavioral Health Pavilion

- We will explore associations with dependent variables and predictor variables by performing bivariate analyses of “Interest in learning more about contraception during your hospital stay” and “Interest in starting a contraceptive during your hospital stay” with predictor variables from surveys and EHR variables using Chi square for categorical variables and Students T-test for continuous variables.
- We will regress significant predictor variables ($p < 0.1$) on dependent variables to determine predictors of “interest in receiving contraception counseling during your hospital stay” and “interest in starting a contraceptive during your hospital stay”.

For our second objective the dependent variables are contraceptive prescription/initiation during hospitalization and contraceptive prescription/initiation following discharge.

- We will create derived variables:
 - Initiation any contraceptive (in hospital, in BC4Teens clinic, none)
 - Initiation preferred contraceptive (in hospital, in BC4Teens clinic, none)
 - Time interval (days) between enrollment and contraception prescription/initiation

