 - Initiation of contraceptive not preferred contraceptive (in hospital, in BC4Teens)
- We will perform univariate descriptive analyses on all variables.
- We will examine contraception initiation all among participants by assessing the proportion of participants who initiate any contraceptive in the a) hospital setting, b) in BC4Teens clinic, and c) either hospital or BC4Teens clinic.
- We will examine contraception initiation all among participants by assessing the proportion of participants interested in contraception care who initiate any contraceptive in the a) hospital setting, b) in BC4Teens clinic, and c) either hospital or BC4Teens clinic.
- We will examine how time between enrollment and Initiation any contraceptive varies by location of contraception prescribing/initiation using Student’s T test.
- We will also perform the 3 analyses above on the variable “initiate preferred contraceptive”
- We will examine the type of contraceptive method prescribed/initiated in the a) hospital setting, b) in the BC4Teens clinic setting, and c) either hospital or BC4Teens clinic
- We will examine variation in type of contraceptive method prescribed/initiated between the hospital setting and the BC4Teens clinic setting using Chi square.
- We will explore associations with dependent variables and predictor variables by performing bivariate analyses of “initiation

PROTOCOL TITLE: Evaluation of Contraception Care @ Behavioral Health Pavilion

any contraceptive” and predictor variables from surveys and EHR variables using Chi square for categorical variables and Students T-test for continuous variables.

- We will regress significant predictor variables ($p < 0.1$) on dependent variables to determine predictors of initiation any contraceptive.
- To better understand personal and system-level differences in initiation of contraception during hospitalization and in BC4Teens clinic, we will examine differences in demographics, survey variables of interest, and EHR variables of interest between participants who initiate “any contraceptive during hospitalization” and initiate “any contraceptive in BC4Teens clinic” using Chi square.

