23.0 Resources Available

23.1 Describe the resources available to conduct the research: For example, as appropriate:

- We conservatively estimate that the demand for inpatient hospitalization will be equally present in 2021 and 2022 as it was in 2019. We estimate that at least 1000 adolescents eligible

for our study will be admitted to Nationwide Children's Hospital following units – Psychiatric Unit, Youth Crisis Stabilization Unit, Psychiatric Crisis Department Extended Observation Care Unit and Hospital Pediatrics service. We estimate that 45% will agree to participate in our study. A demonstration that at least 25% of this sample is interested in contraception care during hospitalization will be notable

- A span of 2 years will be dedicated to study recruitment. The time devoted during that span may vary based upon eligible patients per day as well as follow-up survey schedules.
- All research processes will be carried out on the unit at the time of enrollment. The only exception is verbal consent from the parent or guardian of those who are 14. In those cases, consent may be obtained verbally via telephone after receipt of the study information sheet. The follow-up surveys will be sent electronically, and subjects will complete them on their own time.
- We do not anticipate any medical or psychological distress as a result of this study; however, at the time of enrollment subjects will be admitted so they will have access to all medical and psychological services that NCH provides.
- All study staff are required to complete all research training (CITI and NCH specific human subjects training) prior to being added to the IRB. Additionally, staff will be required to undergo study specific education before involvement in study procedures. All education will be tracked on a training log. If there are any changes made to the IRB all staff will also be required to review the changes. The dates of training will be available in the study Training Log.

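### The chi-square test of method type by setting has no method grouping and no exact alternative, so its error rate may drift from nominal if the table of initiators turns out sparse

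*Combined protocol and SAP*

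**What the plan says.** Section 4.1 makes method choice a secondary endpoint: "Secondary endpoints are location of contraception counseling and initiation, and contraceptive method choice". Under the second objective, section 17.1 first describes it by setting ("We will examine the type of contraceptive method prescribed/initiated in the a) hospital setting, b) in the BC4Teens clinic setting", and the two combined) and then tests it: "We will examine variation in type of contraceptive method prescribed/initiated between the hospital setting and the BC4Teens clinic setting using Chi square".

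No other analysis in 17.1 tests method type between settings. The preferred versus not-preferred comparison asks a different question, and the implant control chart follows a trend over time.

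Section 17.1 does not list or group the methods for this table, has no rule for small expected counts, and names no exact or Monte Carlo test. Initiation is derived by place ("Initiation any contraceptive (in hospital, in BC4Teens clinic, none"), but no initiation rate or expected split is given. Section 2.2 marks hypotheses as not applicable, and no alpha is set for this test.

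**The concern.** The table contains initiators only, divided by two settings and then by method. Some methods are likely to be rare, and one setting may contribute few starts. The usual chi-square reference distribution is unreliable when many expected counts are small.

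The direction of the error depends on how starts divide between settings. With a roughly even split the test is conservative and can miss a real difference in method mix. With very few starts in one setting it can reject too often. A reader of the p-value could not tell in advance which applies. If grouping or an exact test were chosen only after the table had been seen, that choice would be data-driven.

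**Working it through.** **Inputs from the documents**

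- Eligible pool, section 12.2: "It is expected that 1,000 adolescents will be eligible for the study from 2021-2023".
- Participation, section 12.2: "We estimate that 45% will agree to participate".
- Sample size, section 12.1: "It is expected that 450 participants will be recruited for the study". Check: 1,000 × 0.45 = 450, which reproduces.
- Interest benchmark, section 23.1: "A demonstration that at least 25% of this sample is interested in contraception care during hospitalization will be notable". 450 × 0.25 = 112.5, about 113. This is a floor for a notable result. It is neither a forecast nor an initiation rate.

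**Assumptions (not in the documents)**

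- 30 to 90 initiators, with 113 to 200 as a check.
- Splits from 50:50 to 90:10.
- Six methods with shares 30/5/25/30/7/3%.
- Nominal level 0.05.

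**Step 1: expected counts.** For a setting with n_s initiators and a method with share p_k, E = n_s × p_k.

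- 60 initiators, even split: 30 × shares = 9, 1.5, 7.5, 9, 2.1, 0.9. Three of six are below 5 in each setting, so 6 of 12 cells (50%).
- 60 initiators, 54:6. Hospital: 16.2, 2.7, 13.5, 16.2, 3.78, 1.62 (three below 5). Clinic: 1.8, 0.3, 1.5, 1.8, 0.42, 0.18 (all six). That is 9 of 12 cells (75%).
- Simulated over 30 to 90 initiators, 49-79% of cells fall below 5.

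For every expected count to reach 5, the total must be at least 5 / (share of the smaller setting × p_k):

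- Even split: 5 / (0.5 × 0.05) = 200 for a 5% method; 5 / (0.5 × 0.03) = about 333 for a 3% method.
- 70:30: 5 / (0.3 × 0.05) = about 333; 5 / (0.3 × 0.03) = about 556, more than the whole sample.

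**Step 2: size of the Pearson test at nominal 5%.** Simulated with no true difference, six methods, 40,000 tables per scenario.

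| Split | Initiators | Rejection rate |
|---|---|---|
| Even | 30 / 45 / 60 / 90 | 3.0 / 3.2 / 3.4 / 4.0% |
| 80:20 to 85:15 | 45 or more | about 5-6% |
| About 90:10 | 45 / 60 / 90 / 113 | 8.9 / 7.8 / 6.6 / 6.4% |
| 50:50 to 85:15 | 113 to 200 | 4.1-5.5% |

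Repeat runs gave up to 9.1% in the 90:10 row at 45 to 90 initiators.

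**Step 3: grouped methods.** With three categories at 35/25/40% (assumed), the smallest expected count for 45 initiators split evenly is 22.5 × 0.25 = 5.6. Size is 4.1-5.2% for 45 to 113 initiators at every split from 50:50 to 90:10.

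**Step 4: the alternative.** A permutation version of the Pearson statistic has size of about 4-6% on the six-method mix. It can be slightly conservative with very uneven groups (about 3.4-4.5%). Power was computed for an assumed clinic mix of 55/15/5/15/7/3% against the hospital mix above:

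| Hospital:clinic | Chi square | Permutation |
|---|---|---|
| 45 in total, even | 49% | 56% |
| 60 in total, even | 65% | 69% |
| 45:45 | 86% | 87% |
| 48:12 | 40% | 40% |
| 72:18 | 64% | 63% |
| 54:6 | 24% | 18% |
| 41:4 | 19% | 13% |

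The last two falls mostly reflect removal of the excess rejections seen in Step 2.

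A separate run used seven assumed methods. Fisher-Freeman-Halton and the Monte Carlo version held size at 4.4-5.5%. Under one assumed shift, Fisher-Freeman-Halton gained about 3 to 6 points at even to 70:30 splits. Under a second shift at 48:8, power went from 0.06 to 0.04. Any gain therefore depends on the mix and shift assumed.

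**The case against.** The strongest reply is that every quantity that makes the table sparse is assumed. The documents give no initiator count, split, method list or mix, and the survey and EHR forms (Appendices A-D), which might define categories, are not in the available text. This stands, and it is why the point is conditional. A reader might infer that the table is certain to be too sparse, or that the test is invalid as planned. The documents do not support that: with three grouped methods, or with 113 to 200 initiators and splits up to 85:15, size is close to nominal.

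A reader might also take about 113 as a ceiling on initiators. It is not one. The 25% in section 23.1 is a threshold for a notable level of interest, and section 17.1 also assesses initiation among all participants.

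Nor is inflated type I error the general result. At even splits the error is conservative. Clear inflation on the six-method mix appears when about 10% of starts are in the clinic. That means 4 to 9 clinic starters among 45 to 90 initiators, where no test is very informative.

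It can fairly be said that the plan writes only chi square, that a Monte Carlo Pearson p-value is itself a chi-square test, and that a biostatistician is involved (section 17.4). That makes the gap small to close, but the plan still does not say which reference distribution applies or how methods are grouped.

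Finally, the study is observational and no decision hangs on this p-value. The by-setting description of method type is unaffected. This also stands and limits the importance of the point.

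**Conclusion.** The point holds as a conditional risk of minor consequence. The only between-setting test of a named secondary endpoint is a chi square among initiators, with neither the categories nor a small-count alternative specified.

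With about six ungrouped methods and roughly 30 to 90 initiators, about half or more of the cells have expected counts below 5. The nominal 5% test then runs at about 3-4% (even split), about 5-6% (80:20 to 85:15, 45 or more initiators) or about 6.6-9% (about 10% of starts in the clinic, 45 to 90 initiators). With three categories and 45 or more initiators it stays at about 4-5%.

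These figures rest on the assumed counts, splits, method shares and 0.05 level. A reader might infer that an exact test is always more powerful, but the calculations do not show that. On the six-method mix the gain is confined to roughly even splits with up to about 60 initiators.

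**What to change.** In section 17.1, make two changes for this table before the data are examined:

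1. State the method categories to be compared. This choice largely decides whether the table is sparse.
2. Replace the chi-square wording with the Fisher-Freeman-Halton exact test, or with a Monte Carlo p-value for the Pearson statistic. Either remains valid if the table proves dense.

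The cost is a line or two of text and minor extra computation. Apparent power will be lower when one setting has very few starts, mostly because the inflated rejection rate is removed. Broad categories also give up detail on individual methods, which the descriptive by-setting summary can still show.

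The same wording could be applied to the other initiator-only chi-square comparisons in 17.1 (characteristics by setting, and preferred versus not-preferred method). That extension is optional, and no calculation was made for it.

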2.0 Objectives

2.1 The purpose of this study is to examine interest in receiving contraception counseling and contraception initiation female adolescents hospitalized with mental health disorders.

The primary objectives of this study are to 1) Examine interest in receiving contraception counseling among female adolescents hospitalized with mental health disorders, and 2) Examine contraception initiation among female adolescents hospitalized with mental health disorders.

Multiple secondary objectives will be investigated during the study. They include:

- To assess the proportion of female adolescents hospitalized with mental health disorders that receive contraception counseling or are prescribed/initiate any contraceptive during hospital admission or immediately post discharge.

- To determine predictors of receipt of contraception counseling and contraception initiation among female adolescents hospitalized with mental health disorders
- Assess satisfaction with and person-centeredness of contraception care among participants who received contraceptive counseling

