2.2 State the hypotheses to be tested: N/A

2.3 Of note, this study is externally funded by Merck Inc. The PI has a conflict management plan in place approved by the compliance department.

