6.0 Procedures Involved*

6.1 This is an observational study. The study components include participant surveys, EHR data extracts related to sexual and reproductive health, and statistical process control charts for quality improvement analyses. Three surveys will be administered to participants, the first at the time of enrollment, the second immediately after discharge, and the third four months after discharge.

6.2 Potential participants will be approached during their admission at NCH and invited to participate in the study. If they are interested in participation, they will complete an electronic informed consent via redcap, all study participants will receive a copy of their consent via e-mail. If the participant is 14 years old the coordinator will be required to obtain verbal consent from the parent or guardian via Information Sheet. After the consent process is completed, they will fill out the first study survey while they are admitted to the hospital (see Appendix A). The

PROTOCOL TITLE: Evaluation of Contraception Care @ Behavioral Health Pavilion

subsequent two surveys will be sent electronically via their preferred communication method, which will be determined at enrollment. After the last survey is completed the subject will have completed their portion of the study. This is a study with adolescents as the study population and there will be little parental involvement, there are concerns regarding study retention. We will be providing texts as a communication option for the participants as we believe this will be most successful. If a participant chooses this as their preferred contact method. In order to text participants, we will be utilizing Twilio, an NCH approved application.

Study staff will review responses on the following questions on the baseline survey: if the participant indicates they would like to a) learn more about, b) initiate or change contraception methods, and c) desire for privacy for contraception care. Study staff will notify the patient's clinical team if any of these are positive.

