On the day of discharge, or the first business day after discharge if participant is discharged during the weekend or a holiday, study staff will send the second survey (see Appendix B) to the participants who indicated interest in contraception counseling and initiation via their preferred communication method. The patient will have 1 month to complete the survey. They will receive weekly reminders if the survey is incomplete, and after 1 month the participant will be considered lost to follow up for the first follow-up survey. The third survey (see Appendix C) will be sent to the participants who indicated interest in contraception counseling and initiation 4 months after the patient is discharged from the hospital. Again, the participant will be provided the survey link via their preferred contact method and given 1 month to complete the survey and study staff will provide weekly reminders until completion. Completion of the third survey indicates the patient has completed their portion of the study. After 1 month, if the third survey is incomplete, the patient will be considered lost to follow up.

Additionally, routine data pulls from the electronic health record (EHR) will be generated to gather supplementary data not collected from the subject surveys (see Appendix D).

To ensure optimal readability, prior to the start of the enrollment period for the study we will be sending the surveys through the health literacy department. We will also pilot the surveys to 10-15 adolescent patients, ages 14 years and older, we would like to do this in order to get feedback on survey design, so that we can make necessary changes before enrollment starts. These patients may be approached in the Adolescent Medicine Clinic or may be children of NCH employees or other colleagues.

6.3 We do not anticipate any risks associated with enrollment in the study. All PHI and sensitive information recorded for research will only be available to study staff. Additionally, we will be requesting waived parental consent for participants 15 and older to mitigate any potential conflict between parent and participant due to the sensitive nature of this

study. Please see appendices A, B, and C and D for survey and data collection forms.

6.4 Once a participant enrolls in the study, they will then be prompted to complete the baseline survey (Appendix A).

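### Section 17.1 screens predictors at p<0.1 and refits them on the same participants, so the refit's p-values, estimates and intervals ignore the selection; the direction of the error depends on the unknown pattern of effects

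*Combined protocol and SAP*

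**What the plan says.** Section 17.1 uses the same two steps under both objectives. First, each outcome is compared "with predictor variables from surveys and EHR variables using Chi square for categorical variables and Students T-test for continuous variables". Second, variables with p<0.1 go into a regression. For the second objective this reads "We will regress significant predictor variables ($p < 0.1$) on dependent variables to determine predictors of initiation any contraceptive"; the first objective has the same rule for the two interest outcomes.

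The plan gives no list of candidates, no limit tied to the number of events, no split sample, bootstrap, shrinkage or multiplicity control, and no second cohort. The type of regression is not named. Initiation is defined with three levels, but the plan also reports the "proportion of participants who initiate any contraceptive in the a) hospital setting, b) in BC4Teens clinic, and c) either hospital or BC4Teens clinic", and its last grouping gives an evident yes/no outcome.

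On status, section 2.1 lists as a secondary objective "To determine predictors of receipt of contraception counseling and contraception initiation among female adolescents hospitalized with mental health disorders". Section 2.2 reads "State the hypotheses to be tested: N/A", and section 17.1 introduces the bivariate step as exploration. For the candidate variables, section 6.3 refers to forms ("Please see appendices A, B, and C and D for survey and data collection forms") that are not in the text available here.

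**The concern.** A variable enters the regression because its association in these data was large enough to pass. Fitting it again to the same data and reading the usual p-value and interval treats it as if it had been chosen beforehand. For a weak predictor, a reader of the refit cannot tell a real association from a chance one, and cannot tell how far its odds ratio is off.

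This matters most where events are few, and initiation may be such a case. Study staff notify the "clinical team if any of these are positive", so starting a method may be concentrated among participants who declared interest. The purpose clause of the regression step speaks of determining predictors, and no sentence labels its results as hypothesis-generating.

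**Working it through.** **Inputs from the protocol.** Section 12 gives 1,000 eligible and 45% agreeing: 1,000 × 0.45 = 450, which reproduces the stated sample size. The screen is p<0.1. The only outcome rate mentioned is in section 23.1: "A demonstration that at least 25% of this sample is interested in contraception care during hospitalization will be notable". That is a floor for a notable result, not an expected rate.

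**Assumed, because the text gives no values.** 40 candidates, pairwise correlation 0 or 0.2, four true predictors with odds ratio 1.4 per SD, 36 nulls, and initiation in 5–15% of participants.

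**Events.**
- Interest at the floor: 450 × 0.25 = 112.5.
- Initiation, if only interested participants start a method and uptake among them is 20%, 40% or 60%: 112.5 × 0.2 = 22.5, × 0.4 = 45, × 0.6 = 67.5. These are 5%, 10% and 15% of 450.

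**Chance variables, independent candidates.**
- A null passes with probability about 0.10 and has p<0.05 with probability about 0.05, so P(p<0.05 | passes) is about 0.05/0.10 = 50%. Simulation of the screen and refit gives 45–46%.
- Over all nulls: 0.10 × 0.45 = 0.045, about 5%.
- Per dataset: 36 × 0.045 ≈ 1.6 false predictors (simulated 1.7 at a 25% outcome). Fitting all 40 candidates without a screen gives 2.3.

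**True effects that pass, independent candidates.** One variable alone shows the mechanism. With SE ≈ 1/√(450·p·(1−p)) and d = ln(1.4)/SE, the expected estimate among those that pass is 1 + φ(1.645−d)/(d·Φ(d−1.645)) times the truth. The full multivariable screen and refit, which this formula leaves out, gives somewhat more.

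| Outcome rate p | SE | d | Formula | Simulated screen and refit |
|---|---|---|---|---|
| 25% | 1/√84.4 = 0.109 | 3.09 | 1.05 | about 1.10 |
| 10% | 1/√40.5 = 0.157 | 2.14 | 1.24 | about 1.29 |
| 5% | 1/√21.4 = 0.216 | 1.56 | 1.55 | about 1.64 |

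Coverage of the nominal 95% interval for these effects stays at 96–97%, falling to 93–95% at 22.5 events. A separate run with 20 binary candidates shows the same pattern for a weaker effect: a true odds ratio of 1.3 that passes reads about 1.66 at a 25% outcome and 1.95 at 10%. An odds ratio of 3.0 at a 25% outcome reads 3.07, with 95% coverage.

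**Correlation 0.2 between candidates, 25% and 10% outcomes.**

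| Signs of the four effects | Passing effects relative to truth (log-odds) | Passing nulls with p<0.05 |
|---|---|---|
| Two and two | 10–12% and 25–30% too large | about 25% |
| Three against one: the three | 0.76–0.86 | 3–5% |
| Three against one: the lone one | about 1.6 and 1.9 | as above |
| All one sign | 0.95–0.96 and 0.85–0.90 | 2% |

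In the three-against-one case the lone predictor passes in only about a third (25% outcome) or a fifth (10% outcome) of datasets. Its interval then covers the truth in 69–72% or 62–65% of them. When all effects share a sign, about 30 of 40 candidates pass at 25% (112.5/30 ≈ 3.8 events per variable) and 21 at 10% (45/21 ≈ 2.1).

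**The case against.** The strongest reply is that this is an observational study with no hypotheses, that the step is introduced as exploration, and that screening does no worse than the obvious alternative. Much of that stands. The 45% figure is close to the ratio of the two thresholds, and per candidate the error rate stays near 5%. With independent candidates the screen gives fewer false predictors than fitting everything (1.7 against 2.3). Strong predictors come through almost unchanged. At a 25% outcome the inflation of about 10% comes with sound coverage, and if interest were 40–50% it would be only 5–6%.

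A prespecified short list is also not clearly better. With independent candidates and a 25% outcome, a list that misses two of the four true predictors finds 1.7 real ones per dataset, against 3.3 with the screen. At correlation 0.2 its estimates are off by 14–24% unless the omissions cancel. Section 16.1 itself describes the field as little studied, so a complete list is doubtful.

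The reply does not remove the defect. In every setting the refit output ignores how its variables were chosen, and the sponsor cannot know beforehand which pattern of effects applies. The exploratory wording belongs to the bivariate step; the regression step and section 2.1 claim more.

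**Conclusion.** The concern holds, at minor to moderate weight. Naive p-values, estimates and intervals for weak predictors in the refitted models are not reliable as reported, most of all if initiation events are few. With independent candidates, or signs that balance, the error is inflation. With correlated candidates and mostly same-sign effects, it is shrinkage of the majority, with a lone opposite effect mostly lost or, when kept, badly overstated.

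Three stronger readings are tempting and are not supported:
- That the screen creates extra false predictors. Testing many candidates creates them, and the screen yields fewer than the full model.
- That reported odds ratios will generally be too high. This fails when effects mostly share a sign, and the documents say nothing about signs or correlations.
- That the study's main results are at risk. The primary proportions do not use these models.

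The sizes rest on assumed candidate numbers, correlations, effect sizes and initiation rates. The forms that would bound the candidate pool were not available, and this is not counted against the plan.

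**What to change.** Change the analysis text in section 17.1 for both objectives:

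1. Keep the bivariate tables as description, and report results for all candidates, not only those that pass.
2. Repeat the whole procedure, screen plus refit, in bootstrap samples. Report each variable's selection frequency and an optimism-corrected or shrunken estimate in place of the naive refit p-value.
3. Replace the purpose clause of the regression step with hypothesis-generating wording, for example: *These models are hypothesis-generating; variables that are retained are candidate predictors for confirmation in other data.*
4. Add one sentence naming the model, for example: *Interest (yes/no) and initiation in either setting (yes/no) will each be analysed by logistic regression.*

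The cost is a little more analysis and results that look less decisive. Design, recruitment and data collection do not change.

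Optional, as a trade-off and not a requirement: a short list fixed before analysis and sized to the observed events. At a working assumption of 10 events per variable, that is about 11 variables for interest at 112.5 events and about 2 to 7 for initiation at 22.5–67.5. It removes the selection bias, but at the cost described above in missed predictors and omitted-variable bias.
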